5.1 Background of the study

<Current context of pressure ulcers>

Pressure ulcer is a state that is caused by application of persistent and repeated pressure on any part of body, but mostly upon the protruding part of the bone, resulting in poor blood circulation and tissue death. As a common cause of such symptoms is pressure, it is more appropriately termed as a pressure ulcer. This has been a persistent issue not only domestically but overseas, and more and more attention is being paid to prevention and treatment of pressure ulcers, in particular in aging societies, due to rising social and medical expenses caused by pressure ulcers.

Development of pressure ulcer causes physical and mental suffering to a patient as well as financial losses due to increased treatment and hospitalization duration, so that appropriate treatment is necessary. Pressure ulcer is healed through 1-4 steps; during Step 1, non blanching erythema disappears; during Step 2, re-epithelization takes places and the wound is covered with epithelial cells; and during Steps 3-4, the lesion is filled with a new connective tissue and covered with new epithelial cells.

<Medifoam® and Betafoam®>

Medifoam® is a dressing that can be used for burn, pressure ulcer, or serious wounds by providing a wet environment to the wound and thereby protecting the wound and promoting recovery. Medifoam® consists of 3 polyurethane layers and each plays a role of a protective layer, absorption layer, and wound-contacting layer. The protective layer protects the polyurethane layer from external infection and prevents infiltration of infectious microorganism, and maintains the optimal moisture vapor transmission rate(MVTR) to provide a wet environment to the wound (MVTR mean 811 g/m²/day). The absorption layer provides a wet environment to the wound, and immediately absorbs exudates from the wound. The product has the absorption capacity of ≥13.5-fold of the pre-absorption weight, and the moisture retention capacity of ≥6-fold. The wound-contacting layer has a mean 25-75 μm pore size (similar to fibroblasts and keratinocytes), and prevents newly formed epidermis from penetrating into the wound-contacting layer of the product or being removed while changing the dressing. As a result, damage to the recovering wound during the dressing change can be minimized, enhancing prompt wound recovery. Furthermore, as the layer is not adhesive to the wound, exudates can be absorbed effectively and the dressing can be changed while causing less physical and mental suffering.

Currently, Medifoam® is available as various formulations, including a foam type for a wound with oozing, a hydrocolloid type for relatively little oozing or exposed wound, and a liquid type for a wound requiring waterproof protection, so that they can be customized by wound type and lesion.

Meanwhile, Genewel Co., Ltd., the manufacturer of Medifoam®, newly developed povidone-iodine

containing polyurethane foam named Betafoam®. Povidone iodine(PVP-I) is known as a very effective local antibacterial agent and has been widely used as an effective disinfectant for various wounds. PVP-I has a broad antibacterial therapeutic window against bacteria, acid fast bacilli, fungus, protozoa, and viruses, and can be used to treat both acute and chronic wounds. Betafoam® is essentially a polyurethane foam dressing recognized for its effectiveness in various wounds. Based on characteristics of PVP-I and a foam dressing, Betafoam® is expected to support a routine wound healing process while also reducing the risk of wound infection.

<Summary of clinical study results>

(1) Medifoam N

Among 80 burn patients who received a split-thickness skin graft, half of the grafted donor sites were covered with Medifoam N and the other half were covered with Vaseline gauze dressings. Two days after the procedure, dressings were removed, and it was monitored everyday whether epithelization occurred or any complication developed. Results indicated that it took an average of 10.1 days in the Medifoam N group and 13.0 days in the control group, and 80 subjects recovered with no serious complications.

(2) Medifoam Silver

Medifoam Silver was investigated for the effectiveness in re-epithelization in 31 patients with 2- or 3-degree burns with a wound area of 12.6% and 24 patients with a skin graft donor site and a wound area of less than 1.000 cm². In 27 burn patients, re-epithelization was achieved in mean 18.6 days (5-29 days). In 4 patients, it took mean 14.3 days (12-18 days) until an eschar fell off. In 24 patients with a skin graft donor site, successful re-epithelization was achieved after mean 9.5 days (7-15 days) following skin graft. During this period, no complication or side effect occurred and exudates were absorbed well.

This medical device is registered product and currently in use for burn, skin graft, lacerated skin, surgical wound as well as pressure ulcer in clinical field. Clinical trials in burn, skin graft, wound, surgical wound have been done and confirmed the efficacy among those indications. However, clinical trial data on pressure ulcer is not adequate (refer to 8. BETAplast™ PRODUCT MONIGRAPH on protocol reference 24). Therefore, this pilot study is designed to figure out the efficacy of this device on pressure ulcer and additional clinical trial will be conducted upon using the result of this study.

(3) Medifoam H

Medifoam H and DuoDERM were used for 7 days on 66 various wounds including laceration, abrasion, mild burn, and surgical wounds. In some patients, Medifoam H caused mild pruritus when compared to DuoDERM. In terms of exudate improvement, both groups achieved improvement, and the extent of improvement from baseline (pre-dressing) was 82% for Medifoam H and 67% for DuoDERM.

Based on these results, it was planned to apply each of Medifoam[®] and Betafoam[®] to subjects with pressure ulcer, and exploratively observe efficacy of two study devices at the pressure ulcer.

5.2 Study objectives

This aim of this study is to exploratively assess the efficacy and safety of hydrophilic polyurethane foam in pressure ulcer patients.

For this purpose, the percentage of completely healed patients and the time to complete healing will be assessed after applying a study device, Medifoam[®] or Betafoam[®], for 12 weeks to pressure ulcer patients. In addition, the pressure ulcer size reduction rate over 12 weeks will be evaluated.

6. Investigational devices

6.1 Study device 1

- Brand name: Betafoam[®] (Mundipharma)
- Generic name: Polyurethane, povidone iodine
- Indications of use: This product is an absorbent foam dressing, used for secondary care of pressure ulcers, venous ulcers, diabetic ulcers, burns, donor sites, bacterial/malignant infection wounds, chronic/acute full/partial thickness losses such as surgical wounds, and wounds with exudates on a thin and rough surface.
- Storage conditions: Store in a sealed container at ambient temperatures (1~30°C), by avoiding direct sunlight and hot and humid conditions.

6.2 Study device 2

- Brand name: Medifoam[®] (Mundipharma)
- Generic name: Polyurethane
- Indications of use: Contamination prevention and protection of wounds
- Storage conditions: Store in a sealed container at ambient temperatures (1~30°C), by avoiding direct sunlight and hot and humid conditions.

6.3 Management of investigational devices

The principal investigator and the investigational device manager (hereafter 'manager') are responsible for receipt · retention · management and return of the medical devices used in a clinical study.

The manager should confirm receipt and the received quantity of investigational devices in writing which should be signed and appropriately managed. Investigational devices should be stored in a locked cabinet with access limited to study site staff, and investigational devices should be applied to subjects only according to the protocol, and the quantity and management of investigational devices provided to each subject should be documented accurately. The monitor should periodically check the inventory retained by the investigator or manager to confirm accountability of used investigational devices. Unused investigational devices will be retained until the sponsor makes a decision on their return or destruction, and upon study completion, all used device packaging, unused investigational devices, labels, and a copy of medical device management records will be submitted to the responsible monitor.

6.4 Packaging and labeling of investigational devices

Investigational devices will be labeled according to the Enforcement Regulations of the Medical Device Act (enforcement date 2015.07.29), Article 43, Attachment, and the label should include the following contents.

<Contents of the label>

1. "For a clinical study"
2. Brand name and model number
3. Lot No. and manufacturing date (can be substituted with an expiry date)
4. Storage conditions
5. Company name of the manufacturer or importer (including names of a manufacturer and a country, in case of commissioned manufacturing or import)
6. "Cannot be used for purposes other than a clinical study"
7. Subject number (if necessary)

7. Study subject

Pressure ulcer patients of the NPUAP Stage III

8. Subject Inclusion and exclusion criteria

This study will involve subjects who meet all of the following inclusion criteria and none of the exclusion criteria.

8.1 Inclusion criteria

- 1) Adults aged at least 19 years old as of the consent date
- 2) Pressure ulcer of the NPUAP (National Pressure Ulcer Advisory Panel) Stage III at screening
- 3) Pressure ulcer size of 3-100 cm² at screening
- 4) Written consent provided by the subject or representative
(In case a subject has more than one pressure ulcers that meet all inclusion criteria, the largest one is selected as a target lesion.)

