8.2 Exclusion criteria

- 1) Any study ulcer of the NPUAP Stage I, II or IV
- 2) Diabetic ulcer or Venous ulcer (or stasis ulcer)
- 3) Past history of surgical treatment within 1 year or irradiation at the target pressure ulcer within 1 year
- 4) Hypersensitivity reaction to this product or povidone-iodine
- 5) Hyperthyroidism or thyroid disorder requiring drug treatment
- 6) Signs of a current underlying systemic infection (sepsis/bacterial infection/tuberculosis) or cellulitis or osteomyelitis
- 7) Type 1 diabetes
- 8) Current malnutrition
- 9) Heavy smoker: Current smoking level of ≥ 1 pack (20 cigarettes)/day of tobacco
- 10) Drug or alcohol addiction
- 11) Requirement of immunosuppressants during the study or current chemotherapy or radiotherapy
- 12) Application of other investigational product/medical device within 1 month prior to the

investigational device application (1d)

13) Pregnant or breastfeeding women

14) Other renal, hepatic, neurological, immunological disorder that may interfere with the wound healing process, at the discretion of the investigator

9. Target number of subjects and the rationale

The target number of subject enrollment is 20 subjects, with 10 subjects per group.

This study has a purely explorative goal so that no formal sample size calculation will be conducted but it was planned to enroll 10 subjects per group as the minimum sample size to achieve study objectives from a scientific perspective.

- ✓ Medifoam group: 10 subjects
- ✓ Betafoam group: 10 subjects

Even if a subject is withdrawn from the study, the subject will not be replaced.

10. Study method

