10.1 Study design

[figure not shown]
This is a single-center, randomized, 2-arms, open-label pilot study.

Subjects who consent to the study will be assessed for eligibility with screening tests. Subjects can have a 2-week screening period.

After screening, subjects who meet the inclusion/exclusion criteria will apply Medifoam[®] or Betafoam[®] for 12 weeks, after randomization. Targeted subjects are outpatient clinic or hospitalized patients. Subjects will make once weekly site visits.

During the treatment period, dressing is performed twice weekly, but additional dressing changes are allowed, depending on the condition of the pressure ulcer, such as excessive exudates at the study ulcer. Nevertheless, the frequency of additional dressing is limited to twice per day. On the weekly site visit days, the investigator (or clinical research coordinator) will change the dressing; on other occasions, the subject or guardian will perform self-dressing. Subjects who achieve complete healing of the target pressure ulcer within 12 weeks will have early completion.

Efficacy assessment is conducted for a total of 12 times at a 1-week interval, after the investigational device application (8d, 15d, 22d, 29d, 36d, 43d, 50d, 57d, 64d, 71d, 78d, 85d). At each efficacy assessment, the investigator (or clinical research coordinator) should take a digital photograph of the target pressure ulcer and retain it as a source document.

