10.3 Subject enrollment method

As this study will enroll 10 subjects per group without using a control group through randomization. Note that it was planned to enroll 10 subjects per group as follows, as the minimal sample size to achieve study objectives from a scientific perspective.

	Group A	Group B
Study device	Medifoam [®]	Betafoam [®]

Subjects will be enrolled to a Medifoam group and a Betafoam group by randomization to reduce the possible bias which may be caused by the investigator, and once 10 subjects are enrolled in each group, no further enrollment will take place. In addition, even though a subject is withdrawn during the study, the subject will not be replaced.

Clinical Research team of this trial will request to create Randomization List to independent statistician (person in charge of randomization) who is not involving in this study. Randomization list contains the information of subjects assigned upon randomization code. A person in charge for randomization will create and operate Randomization list independently.

Randomization will be generated by randomization program of SAS system. And the permutation of random numbers (random number of A and B) will start from number 1 in consecutive order (i.e. A: Group A, B: Group B). Block size won't be stated in this protocol.

The site will assign the following number to subjects in the order of signing the Informed Consent Form.

Screening Number SXY (X: Site number/A, Y: Serial Number in two digits / 01, 02, 03~)
(i.e. : SA01, SA02, SA03, SA04,...)

Investigator will grant assigned number to the appropriate subject who is eligible for inclusion/exclusion criteria in consecutive order, and the subject will go through randomization. And proper investigation device will be applied to the subject upon assigned group.

Assigned Number RXY (X: Site number/A ; Y: Serial Number in two digits / 01, 02, 03~)
(i.e. : RA01, RA02, RA03, RA04,...)

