### Analysis of Efficacy Endpoints

#### (1) Analysis of endpoints of main interest

- ① For subjects achieving complete healing within 12 weeks, present frequency and percentage. Fisher's exact test will be performed to compare Medifoam and Betafoam treatment groups.
- ② For the time to 100% complete healing, analyze using the Kaplan-Meier method. Time table for subjects to 100% complete healing will be presented and the survival Plot will be shown as a figure. Subjects not achieving 100% complete healing within 12 weeks will not be considered for evaluation for end point of main interest though ulcer size reduction will be evaluated for those subjects.

- ③ For the pressure ulcer size by each time point, present the mean, median, min, max and standard deviation. t-test will be conducted to compare Medifoam and Betafoam, and paired t-test will be used to see the difference between each post visit and baseline(1d).
- ④ For the pressure ulcer size reduction rate, present the mean, median, min, max and standard deviation. t-test will be conducted to compare Medifoam and Betafoam.
- ⑤ For the analysis for efficacy, conduct sub-analyses by use of topical antibiotics and glucocorticoids for the pressure ulcer during the study. t-test will be performed to compare Medifoam and Betafoam, and paired t-test will be used to see the difference between post visits and baseline(1d).

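### The SAP compares raw ulcer size between arms at each visit without adjusting for 1d area, although eligible ulcers span 3–100 cm² and there are 10 subjects per arm

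*Protocol*

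**What the plan says.** - **Eligibility.** Protocol 8.1 requires "Pressure ulcer size of 3-100 cm² at screening". The SAP repeats this.
- **Duration and numbers.** Devices are applied "for 12 weeks, after randomization" (Protocol 10.1). Protocol section 9 states: "The target number of subject enrollment is 20 subjects, with 10 subjects per group". It adds that "no formal sample size calculation will be conducted".
- **Allocation.** "Subjects will be enrolled to a Medifoam group and a Betafoam group by randomization" (Protocol 10.3). The list comes from SAS, the block size is withheld, and no stratification factor is named.
- **Ulcer size.** Absolute size by visit is a main endpoint in the SAP only (section 7.1). For it, SAP section 8 item 3 specifies "t-test will be conducted to compare Medifoam and Betafoam, and paired t-test". The Table 0603 footnote also lists a Wilcoxon rank sum test. Neither test takes a covariate.
- **Reduction rate.** This is a main endpoint in both documents. It is the fall in area from 1d divided by 1d area, and the arms are compared by t-test (Table 0604).
- **Healing.** "Fisher's exact test will be performed to compare Medifoam and Betafoam treatment groups" (SAP section 8 item 1, Table 0601), unadjusted.
- **Starting size elsewhere.** Table 0502 gives screening length and width by arm. Table 0603 has a 1d row, and its title includes change from 1d. The only sub-analyses are by topical antibiotics and glucocorticoids.

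**The concern.** An ulcer's area at a later visit depends heavily on its area at 1d. When starting areas can differ 33-fold and each arm has 10 subjects, a between-arm difference in cm² mixes any device effect with whatever difference in starting area the allocation produced. Even in a well-balanced trial, the spread of starting areas stays in the error term and hides real differences.

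The study is exploratory, but Protocol 5.1 says that a further trial will build on its results. The SAP also puts a between-arm p-value on raw size at every visit, although Protocol 16.2 plans no formal test. A reader of Table 0603 could take a starting difference for a device effect, or miss a device effect in the noise.

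**Working it through.** The plan gives no power, SD or healing rate, so there is no stated figure to reproduce.

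**Inputs from the documents:** area 3–100 cm² (100/3 = 33.3-fold) and 10 per arm.

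**Assumed:** the distribution of area, the link between 1d and later area, and two-sided 0.05 (the SAP gives 0.05 only for its normality test).

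**1. Chance imbalance, log-uniform areas**
- SD of ln(area) = ln(100/3)/√12 = 3.507/3.464 = 1.012.
- SE of the arm difference in mean ln(area) = 1.012 × √(2/10) = 0.453.
- Geometric means at least 1.5-fold apart: P(|Z| > 0.405/0.453) = 0.37.
- At least 2-fold apart: P(|Z| > 0.693/0.453) = 0.13.

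**2. Planned tests with no true effect.** The simulation used 100,000 trials of 10 v 10 with simple allocation. Later area = 1d area × a residual fraction, lognormal with median 0.5 and log-SD 0.5. The model has no ulcers at exactly 0 cm².

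| Assumed areas on 3–100 cm² | 2-fold or greater imbalance | Size t-test significant, all trials | Size t-test significant, given 2-fold or greater | Reduction-rate t-test, given 2-fold or greater | Log-area ANCOVA, given 2-fold or greater |
|---|---|---|---|---|---|
| Log-uniform | 12.5% | 3.9% | 23.2% | 4.4% | 5.0% |
| Uniform | 4.7% | 4.5% | 29.9% | 4.7% | 4.9% |
| Lognormal (median 10, log-SD 1), truncated | 5.0% | 3.6% | 32.9% | 5.0% | 4.9% |

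The overall error rate stays below 5%, but false positives gather where the arms start apart. With log-uniform areas, 0.125 × 0.232 = 0.029 of the 0.039 total comes from allocations with 2-fold or greater imbalance.

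The reduction rate is unaffected here because the model makes percent healing independent of starting area.

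**3. Precision.** Let r be the correlation of 1d and later area (assumed). Adjustment cuts the standard error by 1 − √(1 − r²) against raw size. Against change from 1d with equal variances, the cut is 1 − √((1 + r)/2).

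| r | Against raw size | Against change from 1d |
|---|---|---|
| 0.5 | 13% | 13% |
| 0.7 | 29% | 8% |
| 0.9 | 56% | 3% |

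In the model of step 2, power to detect a 40% smaller residual area is 11–23% with the planned t-test, 15–22% with a t-test on log area, and about 56% with log-area ANCOVA. The gain over the t-test on log area comes from adjustment alone.

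**4. Healed percentage.** The assumed model is logistic in ln(area), with about 40% healed overall. With no true effect, a 2-fold or greater imbalance gives an expected gap of 9–10, 17–19 or 23–24 points for slopes of 0.5, 1.0 or 1.5. Fisher's test is significant in 1.2–1.3% of trials overall, and in at most about 6% under such imbalance.

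**The case against.** The strongest reply has four parts.

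- **The protocol's own size endpoint is already relative to 1d.** Raw size is a SAP addition. This stands, and it confines the main defect to item 3 and Table 0603. The protection is full only if percent healing does not depend on starting area, which the documents do not establish.
- **Table 0603 is titled to include change from 1d.** A between-arm comparison of change is plausible, because the vital-sign shells (Tables 0901 and 0902) print one. The Table 0603 shell is abbreviated and shows none, and item 3 describes the between-arm test for size. If change is compared, the precision gain is the smaller column in step 3.
- **Randomisation protects the type I error, and starting size is displayed.** Both are true. Display lets a reader see an imbalance but does not correct the estimate.
- **The study is a declared pilot, and every magnitude is assumed.** This also stands and keeps the point modest. It is no reason to prefer the less precise analysis when 1d area is already recorded.

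A reader might go further and infer that allocation must be stratified by area. The documents do not support that. Protocol 10.3 stops enrolment at 10 per group. Two strata with incomplete blocks of 4 could end 8:12. The benefit would depend on a healing gradient that the documents do not give. With 20 subjects, stratification is a trade-off and its absence is not a defect.

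**Conclusion.** The between-arm comparison of raw size at each visit should be adjusted for 1d area. As planned, it is valid on average over allocations. It is imprecise, though, and it can mislead in a trial whose arms start apart: a 2-fold or greater difference arises in 5–13% of allocations, and the test is then significant in about 23–33% with no device effect. These figures rest on three assumed area distributions and a multiplicative healing model. They apply to the t-test; the Wilcoxon alternative is equally unadjusted but was not simulated.

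A reader might infer that starting size undermines every main endpoint. That goes too far. The reduction rate is largely protected on the condition given above. For healing, Fisher's test stays conservative and the risk lies in how the percentages are read. At 40% healed in both arms, sampling error alone gives the difference an SD of √(2 × 0.4 × 0.6/10) = 22 points. Small numbers therefore limit that endpoint whatever is done about area.

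**What to change.** **SAP section 8 item 3 and Table 0603.** Replace the between-arm t-test on raw size by a baseline-adjusted difference with its confidence interval: ANCOVA on 1d area, preferably with both areas on the log scale. State in advance how healed ulcers at 0 cm² are handled, for example by a small fixed offset or a rank-based ANCOVA.

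**SAP section 8 item 4 and Table 0604.** Add 1d area as a covariate for the reduction rate.

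**Table 0601.** Show healed numbers descriptively by 1d area band, with the bands fixed before the data are seen.

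Leave the randomisation as it is. The cost is one degree of freedom per model, the rule for zeros, and SAP and table-shell wording. Area is already measured at 1d (Protocol 12.1.2), so no new data, visits or subjects are needed.
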